3.7 Protocol Deviations

As this is a real-world study, the chances of protocol deviations occurring in this study are minimal and limited to data breaches, deviations to Good Clinical Practice, or treatment outside of the parameters of the Abilify MyCite US package insert.

In the event of a significant deviation from the protocol due to an emergency, accident, or mistake (eg, violation of informed consent process or patient enrolled in violation of eligibility criteria), the study physician will notify HealthCore, who will contact the sponsor at the earliest possible time by telephone. The study physician and sponsor will come as quickly as possible to a joint decision regarding the patient's continuation in the study. This decision will be documented by the study physician and the sponsor.

4 Reporting of Adverse Events

In this phase 4 study, all SAEs (ie, drug-related SAEs and device-related SAEs), device-related nonserious AEs (ie, related to the device component of Abilify MyCite treatment, including those leading to withdrawal from Abilify MyCite), potential hepatotoxicity cases, and pregnancies will be monitored and collected. For device-related AEs leading to withdrawal from Abilify MyCite, the reason for withdrawal will be collected.

4.1 Definitions

4.1.1 Drug-related Serious Adverse Events

A serious adverse event (SAE) includes any event that results in any of the following outcomes:

- Death
- Life-threatening; eg, the patient was, in the opinion of the HCP, at immediate risk of death from the event as it occurred. It does not include an event that, had it occurred in a more severe form, might have caused death.
- Persistent or significant incapacity/disability or substantial disruption of the ability to conduct normal life functions.
- Requires inpatient hospitalization or prolongs hospitalization.
 - Hospitalization itself should not be reported as an SAE; whenever possible the reason for the hospitalization should be reported.
 - Hospitalizations or prolonged hospitalizations for social admissions (eg, those required for reasons of convenience or other non-medical need) are not considered SAEs.
- Congenital anomaly/birth defect.
- Other medically significant events that, based upon appropriate medical judgment, may jeopardize the patient and may require medical or surgical intervention to prevent one of the outcomes listed above; eg, allergic bronchospasm requiring intensive treatment in an emergency room or home, blood dyscrasias or convulsions that do not result in hospitalization, or the development of drug dependency or drug abuse.

4.1.2 Device-related Serious Adverse Events

A device-related SAE is defined as:

- An event that reasonably suggests that a device has or may have caused or contributed to a death or serious injury.
 - Contributed to is defined as a death or serious injury that was or may have been attributed to a medical device, or that a medical device was or may have been a factor in a death or serious injury, including events occurring as a result of any of the following:
 - Failure;
 - Malfunction;
 - Improper or inadequate design;
 - Manufacture;
 - Labeling;

- User error.
- Serious injury means an injury or illness that includes any of the following:
 - Is life-threatening.
 - Results in permanent impairment of a body function or permanent damage to a body structure.
 - Necessitates medical or surgical intervention to preclude permanent impairment of a body function or permanent damage to a body structure. Permanent means irreversible impairment or damage to a body structure or function, excluding trivial impairment or damage.
- Any of the following events that manufacturers or importers become aware of that reasonably suggests that one of their marketed devices:
 - May have caused or contributed to a death or serious injury.
 - Has malfunctioned and that the device or a similar device marketed by the manufacturer or importer would be likely to cause or contribute to a death or serious injury if the malfunction were to recur.

For the purpose of this study, device-related SAEs include any event that is related to the IEM, patch, or the phone and application (reported to Otsuka).

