4.1.3 Nonserious Adverse Events

Nonserious AEs are all AEs that do not meet the criteria for a "serious" AE ([Section 4.1.1](#) and [Section 4.1.2](#)). As described above, only nonserious AEs that are related to the device (ie, related to the device component of Abilify MyCite, including those leading to withdrawal from Abilify MyCite) will be collected in this study.

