4.1.4 Immediately Reportable Event

Immediately reportable events (IREs) include the events discussed in [Section 4.1.1](#), [Section 4.1.2](#), and any of the following outcomes:

- Any SAEs;
- Any AEs related to occupational exposure;
- Any device-related nonserious AEs, including skin irritation that is Grade 2 or worse (see [Appendix 9](#)), ie, definite erythema that is readily visible; minimal (or worse) edema or minimal (or worse) papular response;
- Potential drug-induced liver injury (DILI) case (see [Section 4.4](#));
- Pregnancies are also defined as IREs. Although normal pregnancy is not an AE, it will mandate Abilify MyCite discontinuation and must be reported on an IRE form to the sponsor. Pregnancy will only be documented as an AE in the data collection tool, if there is an abnormality or complication;

If a patch-related nonserious AE occurs, the skin irritation scale should be completed; Grade 2 or above on the scale are considered medically significant for purposes of reporting.

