5.3.1 AEs

For the purpose of this study, AEs that do not meet the definition for a “serious” AE (section 4.1.1 and section 4.1.2 of the protocol) will only be collected if they are device-related (i.e., related to the device component of Abilify MyCite, including those leading to withdrawal from Abilify MyCite.)

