5.3.2 SAEs

All AEs meeting the definition of drug-related SAE (section 4.1.1 of the protocol) and device-related SAE (section 4.1.2 of the protocol) will be collected.

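### The last sentence of protocol 4.1.2 makes any event related to the marker, patch, phone or app a device-related SAE, contradicting the nonserious device-event category used elsewhere

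*Protocol*

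**What the plan says.** Protocol 4.1.2 first defines a device-related SAE by outcome. The leading criterion is "An event that reasonably suggests that a device has or may have caused or contributed to a death or serious injury"; a malfunction likely to lead to either on recurrence also counts. The description of permanent harm sets a floor, "excluding trivial impairment or damage". The section then closes with a study-specific sentence: "device-related SAEs include any event that is related to the IEM, patch, or the phone and application (reported to Otsuka".

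Protocol 4.1.3 defines the other side by exclusion. It begins "Nonserious AEs are all AEs that do not meet the criteria for a" serious event, refers back to 4.1.1 and 4.1.2, and then collects "only nonserious AEs that are related to the device".

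Protocol 4.1.4 lists among the immediately reportable events (IREs) "Any device-related nonserious AEs, including skin irritation that is Grade 2 or worse".

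The SAP takes both definitions from the protocol. SAP 5.3.1 says that events not meeting protocol 4.1.1 or 4.1.2 "will only be collected if they are device-related". SAP 5.3.2 says that an event meeting the definition of "device-related SAE (section 4.1.2 of the protocol) will be collected".

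**The concern.** The closing sentence of 4.1.2 has no seriousness condition, and its position and study-specific wording make it look like the rule to apply. One site could follow it and record transient patch erythema as an SAE. Another could follow 4.1.4 and record the same event as nonserious.

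Classification matters in two ways. First, the safety analysis is purely descriptive (protocol 7.4, SAP 5.3), so any count of SAEs depends directly on how sites classify. Second, some follow-up duties are stated only for SAEs: after withdrawal (protocol 3.6.3), until return to baseline or normal values, or until otherwise explained (4.3), until resolved or stabilized (4.6), and for new events after the last scheduled contact that are judged associated with the product (4.6.1).

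**Working it through.** No arithmetic applies to the core point, because the plan states no figure for it. The check is whether the definitions can all hold together.

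**Step 1. The definitions as sets.** Let D be all device-related events. Let S1 be events meeting 4.1.1 and S2 events meeting 4.1.2. By 4.1.3 and SAP 5.3.1, the nonserious events to be collected are N = D and not (S1 or S2).

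**Step 2. Apply the closing sentence of 4.1.2 literally.** S2 then contains every event related to the ingestible event marker (IEM), the patch, or the phone and application. N keeps only device-related events from a component not on that list. Protocol Section 1 names one such component, the web portal for providers and caregivers, which is an unlikely source of a patient's adverse event. So N is essentially empty, though not strictly so.

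**Step 3. Follow one event, mild patch erythema with no other consequence.**

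| Text | Result |
|---|---|
| 4.1.2, outcome criteria | Not an SAE: no death, no serious injury |
| 4.1.2, closing sentence | SAE: related to the patch |
| 4.1.3 | Cannot be nonserious once it meets 4.1.2 |
| 4.1.4 | Nonserious: even Grade 2 or worse skin irritation is placed there, and the section speaks of patch-related nonserious events |
| SAP 5.3.1 and 5.3.2 | Whatever protocol 4.1.1 and 4.1.2 give |

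**Step 4. Check the rest of the protocol.** The opening of Section 4 lists device-related nonserious events separately from SAEs. Section 4.1.7 defines causality for both classes. Section 4.3 names both in its reporting list. Each presupposes that N is not empty, so they cannot stand together with a literal reading of the closing sentence of 4.1.2.

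**Step 5. What changes and what does not.** Under 4.1.4 and 4.3, any device-related nonserious event already goes to the sponsor immediately, by the same routes and on the same form as an SAE. Collection and immediate reporting are therefore the same on either reading. The serious/nonserious label, any count built on it, and the SAE-only follow-up duties differ. The hospitalization endpoint, sample size and power are not touched.

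**The case against.** The strongest reply is that the closing sentence only says which components count as the device, a word left generic above it. It says that device-related SAEs include these events, not that they are defined by them. Read as a test of seriousness, it would make every criterion before it pointless. Four other places in Section 4 keep a nonserious device category, and 4.1.4 speaks directly to patch irritation. The eCRF completion guidelines (protocol 5.2) and site training (protocol 8) may also have told sites how to classify.

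Much of this stands. Component scope is probably what was meant. But 4.1.2 does not say so: it refers to any event, without limiting it to events that meet the criteria above. Nothing else in the protocol or SAP narrows it, and the guidelines and training materials are not part of these documents.

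A reader might infer more than the documents support:

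- **That a nonserious device-event table would be blank.** SAP 5.3 summarizes device-related events as one group by system organ class and preferred term. The visible text plans no separate nonserious table.
- **That trivial patch events would hide serious injuries.** The preferred-term summary and the three-level severity grading in protocol 4.1.6 would still tell them apart.
- **That the inflation can be sized.** The documents give no rate of patch reactions. Assuming 5% to 20% of the planned 640 patients, 640 × 0.05 = 32 and 640 × 0.20 = 128 patients would be affected. That range rests on the assumed rate and on every site following 4.1.2 against 4.1.4, so it is an illustration and not a finding.

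**Conclusion.** The text is wrong as written. The closing sentence of 4.1.2 drops the seriousness condition. Taken literally, it makes a mild patch reaction an SAE and leaves essentially nothing for the nonserious category in 4.1.3 and SAP 5.3.1. It therefore contradicts Section 4 (opening), 4.1.4, 4.1.7 and 4.3. The SAP inherits the conflict through its cross-references and does not resolve it.

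The consequence is limited to classification, SAE counts and SAE follow-up. It would be a mistake to conclude that events go uncollected or unreported. SAP 5.0 also records that the study ended after two patients, with only baseline information summarized, so the practical effect on reported results is small. The contradiction itself follows from the wording alone and rests on no assumed rate.

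**What to change.** Reword the last sentence of protocol 4.1.2 so that it defines the scope of the device and not seriousness, for example:

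*In this study the device comprises the IEM, the patch, and the phone and application. A device-related SAE is an event related to any of these that meets a seriousness criterion in Section 4.1.1 or 4.1.2.*

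Both sections should be cited because inpatient hospitalization is a seriousness criterion only in 4.1.1. Citing 4.1.2 alone would let a device-related hospitalization lose its SAE status. All other device-related events stay in 4.1.3, and SAP 5.3.1 and 5.3.2 then work through their existing references.

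If the sponsor did intend every device event to be an SAE, the change goes the other way: Section 4 (opening), 4.1.3, 4.1.4, 4.1.7, 4.3 and SAP 5.3.1 must be reconciled with that rule.

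For the rewording proposed here, the cost is one sentence in a protocol amendment and a matching line in the eCRF completion guidelines. No new data are needed.

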4.1.3 Nonserious Adverse Events

Nonserious AEs are all AEs that do not meet the criteria for a "serious" AE ([Section 4.1.1](#) and [Section 4.1.2](#)). As described above, only nonserious AEs that are related to the device (ie, related to the device component of Abilify MyCite, including those leading to withdrawal from Abilify MyCite) will be collected in this study.

4.1.4 Immediately Reportable Event

Immediately reportable events (IREs) include the events discussed in [Section 4.1.1](#), [Section 4.1.2](#), and any of the following outcomes:

- Any SAEs;
- Any AEs related to occupational exposure;
- Any device-related nonserious AEs, including skin irritation that is Grade 2 or worse (see [Appendix 9](#)), ie, definite erythema that is readily visible; minimal (or worse) edema or minimal (or worse) papular response;
- Potential drug-induced liver injury (DILI) case (see [Section 4.4](#));
- Pregnancies are also defined as IREs. Although normal pregnancy is not an AE, it will mandate Abilify MyCite discontinuation and must be reported on an IRE form to the sponsor. Pregnancy will only be documented as an AE in the data collection tool, if there is an abnormality or complication;

If a patch-related nonserious AE occurs, the skin irritation scale should be completed; Grade 2 or above on the scale are considered medically significant for purposes of reporting.

4.1.5 Abnormal Clinical Laboratory Test Changes

Clinical laboratory assessments will be conducted at the HCPs' discretion to ensure safety of the patient. Ongoing clinical laboratory assessments are not required for this study.

In the event that the HCP orders a laboratory test in the interest of patient safety, it is the HCP's responsibility to review the results of all laboratory tests as they become available.

Abnormal laboratory tests that a physician deems related to the product would be considered a SAE and/or IRE if they fit the criteria set forth in [Section 4.1.1](#), [Section 4.1.2](#), and [Section 4.1.4](#).

4.1.6 Severity

Adverse events will be graded on a 3-point scale and reported as indicated in the data collection tool. The intensity of an adverse experience is defined as follows:

- 1 = Mild:** Discomfort noticed, but no disruption to daily activity.
- 2 = Moderate:** Discomfort sufficient to reduce or affect normal daily activity.
- 3 = Severe:** Inability to work or perform normal daily activity.

4.1.7 Abilify MyCite Causality

Assessment of causal relationship of an SAE or device-related nonserious AE to the use of Abilify MyCite is defined as follows:

- Related:** There is a reasonable possibility of a temporal and causal relationship between Abilify MyCite and the SAE or device-related nonserious AE.
- Not Related:** There is no temporal or causal relationship between Abilify MyCite and the SAE or device-related nonserious AE.

4.2 Eliciting and Reporting Serious Adverse Events

The HCP will assess patients for the occurrence of SAEs. To avoid bias in eliciting SAEs, patients should be asked the non-leading question: “How have you felt since your last visit?” All SAEs reported by the patient must be recorded on the source documents and data collection tool provided by the sponsor. Serious AE collection is to begin after a patient has signed the ICF. All SAEs will be collected starting from the signing of the ICF until the end of the study.

Use medical terminology in SAE reporting. Serious adverse events should be reported as a single unifying diagnosis whenever possible or, in the absence of a unifying diagnosis, as individual signs or symptoms. Exacerbation or disease progression should be reported as an SAE only if there are unusual or severe clinical features that were not present, or experienced earlier, or not expected based on the course of the condition. An SAE that undergoes a change in severity, seriousness, or toxicity should be reported as a new SAE.

In addition, Clinical Safety and Pharmacovigilance must be notified immediately by telephone, fax, or e-mail of any IREs according to the procedure outlined below, in [Section 4.3](#). Special attention should be paid to recording hospitalization and concomitant medications.

4.3 Immediately Reportable Events

The HCP must immediately report after becoming aware of any SAE, potential DILI, confirmed pregnancy, or any device-related nonserious AEs (which include skin irritation that is Grade 2 or worse per [Appendix 9](#), ie, definite erythema that is readily visible; minimal [or worse] edema or minimal [or worse] papular response) by telephone, fax, or e-mail to Clinical Safety and Pharmacovigilance using the contact information on the cover page of this protocol (see also [Appendix 2](#)). An IRE form must be completed and sent by e-mail, fax, or overnight courier to Clinical Safety and Pharmacovigilance.

Patients experiencing SAEs should be followed clinically until their health has returned to baseline status, or until all parameters have returned to normal or have otherwise been explained. It is expected that the HCP will provide or arrange appropriate supportive care for the patient and will provide prompt updates on the patient’s status to Clinical Safety and Pharmacovigilance.

4.4 Potential Drug-induced Liver Injury

For a patient who receives laboratory tests, if the test indicates an elevation in aspartate aminotransferase or alanine aminotransferase that is ≥ 3 times the upper limit of normal

(ULN), a total bilirubin level should also be evaluated. If the total bilirubin is ≥ 2 times the ULN, an IRE form for be completed, with all values listed.

4.5 Pregnancy

Females of childbearing potential (FOCBP) are defined as female patients or female partners of the male patients for whom menstruation has started and who are not documented as sterile (eg, have had a bilateral oophorectomy and/or hysterectomy or who have been postmenopausal for at least 12 months).

Before study enrollment, FOCBP must be advised of the importance of avoiding pregnancy during study participation and the potential risk factors for an unintentional pregnancy. The patient must sign an ICF stating that the risks and consequences were discussed with her.

During the study, all FOCBP should be instructed to contact the HCP immediately if they suspect they might be pregnant (eg, missed or late menstrual cycle).

If a female patient is suspected to be pregnant before the patient receives Abilify MyCite, the investigator can recommend the patient undergo a pregnancy test with their general practitioner or primary care physician. If the pregnancy is confirmed, the patient must not receive Abilify MyCite and must not be enrolled in the study. If pregnancy is suspected while the patient is taking Abilify MyCite, Abilify MyCite may be continued at HCP discretion until the result of the pregnancy test is known. If pregnancy is confirmed, Abilify MyCite may be continued at HCP discretion based on treatment guidelines for the medication administered. If the HCP discontinues the patient from Abilify MyCite, it must be performed in an appropriate manner (eg, dose tapering if necessary for patient safety) and the patient will be withdrawn from the study. (Exceptions to study discontinuation may be considered for life-threatening conditions only after consultations with the Clinical Safety and Pharmacovigilance department [see the cover page of this protocol for contact information]).

The HCP must immediately notify the sponsor of any pregnancy associated with Abilify MyCite exposure during the study and for 30 days for a female patient, 90 days for female partner of a male patient, after the last dose of Abilify MyCite, and record the event on the IRE form and forward it to the sponsor. Pregnancies of patients or their partners will be followed to term. In the event of pregnancy of a patient's partner, consent to follow the pregnancy will be obtained. The sponsor will forward Pregnancy Surveillance Form(s) for monitoring the outcome of the pregnancy.

Protocol-required procedures for study discontinuation and follow-up must be performed on the patient unless contraindicated by pregnancy (eg, x-ray studies). Other appropriate pregnancy follow-up procedures should be considered, if indicated. In addition, the HCP must report to the sponsor, on appropriate Pregnancy Surveillance Form(s), follow-up information regarding the course of the pregnancy, including perinatal and neonatal outcome. Infants will be followed for a minimum of 6 months from the date of birth.

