3.1.1 Main Study

The study design schematic for the main study is provided in [Figure 3.1-2](#).

This is a phase 4, open-label, prospective, pragmatic clinical trial to assess the difference between all-cause hospitalizations in patients using Abilify MyCite (for Months 1-3, then prohibited for Months 4-6) versus virtual matched controls from baseline to Day 180.

Virtual matched controls ^{CCI} [REDACTED] would be receiving treatment as usual (ie, any product other than Abilify MyCite, which may be oral aripiprazole or any other product).

Eligible patients will enter a screening period of up to 13 days. For patients enrolling into the study, those not on aripiprazole at screening will use the screening period for conversion to aripiprazole from other antipsychotics according to the approved labels. At the baseline visit (which may be the same visit as the screening visit), Abilify MyCite onboarding will be provided in the office, with commercial informational materials and additional call center support; then, patients will initiate 3 months of treatment with Abilify MyCite at the baseline visit.

During the following 3 months (Months 4 through 6), use of Abilify MyCite will be prohibited (and the patient continues with oral aripiprazole or other appropriate treatment, per routine clinical care). The primary endpoint will be assessed at Day 180. The final study visit will be on Day 180 for patients not continuing in the second, optional interventional period.

After the visit at Day 180, a second, optional interventional period (up to 6 months of Abilify MyCite) may be initiated per the joint decision of the patients with their study physician; patients in this second, optional interventional period will have a visit at Day 360 (in addition to their regular visits as clinically indicated). During this second, optional interventional period, patients may start and stop Abilify MyCite as clinically indicated.

Enrolled patients will be matched to a virtual control group identified from ^{CCI} [REDACTED] in a 1:3 ratio (enrolled patients on Abilify MyCite treatment versus virtual matched controls).

^{CCI} [REDACTED]
[REDACTED] the matching will be performed after the Abilify MyCite arm has been completed.

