3.1.2 Exploratory Study

The study design schematic for the parallel exploratory study is provided in [Figure 3.1-3](#). The parallel exploratory study will utilize a different set of physicians and patients from the main study. Results from the exploratory study will be analyzed separately from the main study results.

Procedures for the exploratory study will be similar to those in the main study (see [Section 3.1.1](#)), with the exception that there will be 1-month intervals of Abilify MyCite use (and 1-month intervals of prohibition of Abilify MyCite use), as diagrammed in the study schematic ([Figure 3.1-3](#)). During periods of nonuse of Abilify MyCite, the patient continues with oral aripiprazole, per routine clinical care.

In the exploratory study, each patient will receive Abilify MyCite per 1 one of 2 sequences over a 360-day period:

- Sequence 1: Only in Months 1, 2, 5, and 10.
- Sequence 2: Only in Months 1, 4, 7, and 10.

Sites will be randomized to 1 of the 2 sequences.

For this exploratory study, the site visits will be at screening, baseline (which may be the same day as the screening visit), Day 180, and Day 360; additional visits are to occur as clinically indicated. The exploratory arm will begin after the main study is enrolled at approximately 50% (ie, staggered start).

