3.6.3 Individual Patient

Patient withdrawal from the study will be based upon physician clinical determination and/or patient decision. Participation in the study is voluntary, and all patients are free to terminate their participation at any time. In the event of study withdrawal, the study physician will record the reason for study withdrawal and continue to follow-up with the patient for any unresolved SAEs. Upon patient withdrawal from the study, all data collection will end, but all study data collected up to withdrawal will be included in the study database.

In addition, patients falling under the following criteria must be withdrawn from the study:

- occurrence of any intercurrent illness or abnormality in a laboratory assessment which, in the opinion of the physician, warrants the patient's permanent withdrawal from the study;
- at the request of the patient or physician;
- patient becomes pregnant; or
- patient is lost to follow-up.

3.6.4

CCI

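### Protocol 4.5 lets Abilify MyCite continue after a pregnancy confirmed on product, while 4.1.4 requires it to stop and 3.6.3 requires withdrawal

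*Protocol*

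**What the plan says.** Three sections of the Protocol cover a pregnancy that arises during the study.

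- **Section 4.5 (Pregnancy)**, on a pregnancy confirmed in a patient already taking the product: "If pregnancy is confirmed, Abilify MyCite may be continued at HCP discretion based on treatment guidelines for the medication administered". The next sentence begins "If the HCP discontinues the patient from Abilify MyCite, it must be performed in an appropriate manner" and ends by saying that such a patient will be withdrawn. A parenthesis adds: "Exceptions to study discontinuation may be considered for life-threatening conditions only after consultations with the Clinical Safety and Pharmacovigilance department".
- **Section 4.1.4 (Immediately Reportable Event)** says of normal pregnancy that "it will mandate Abilify MyCite discontinuation and must be reported on an IRE form to the sponsor". It states no discretion.
- **Section 3.6.3 (Individual Patient)** says that "patients falling under the following criteria must be withdrawn from the study" and lists "patient becomes pregnant; or" without a qualifier.

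For a pregnancy confirmed before first use, Section 4.5 bars both treatment and enrollment. That agrees with the exclusion criterion in Section 3.3.5 and is not in question. SAP 5.3.4 says only that pregnancies and their outcomes will be collected.

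**The concern.** Section 4.5 is where a site would look first, and it permits what 4.1.4 forbids. Two sites could handle the same on-product pregnancy differently, and one of them would be acting against the protocol. The rule governs fetal exposure and also a change of treatment in recently hospitalized patients with serious mental illness. About 100 sites were planned (Section 3.3.2), with on-site monitoring only for cause (Section 8), so uneven handling would not be easy to see.

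There is also a smaller data consequence. Under 3.6.3, data collection ends at withdrawal, although data gathered up to that point are kept. The analysis population in SAP 5.1.2 requires a completed Day 180 visit, and the SAP does not say that an early-termination visit counts as one. As worded, a patient withdrawn for pregnancy before Day 180 drops out of that population, while a patient kept in under 4.5 can remain. Inclusion could therefore depend on which section the site followed.

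**Working it through.** **Comparison of the text, for a pregnancy confirmed on product**

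| Question | 4.1.4 | 3.6.3 | 4.5 |
|---|---|---|---|
| May the product continue? | No; stopping is mandatory | Not addressed | Yes, if the physician so decides |
| Must the patient leave the study? | Not addressed | Yes, no condition | Stated only where the physician stops the product |
| Exception for life-threatening conditions? | None | None | Yes, after consultation |

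Sections 4.1.4 and 3.6.3 are compatible with each other; 4.5 departs from both. Because 4.5 permits rather than requires continuation, stopping and withdrawing complies with all three. Continuing the product conflicts with 4.1.4 in every case, and with 3.6.3 as well if the patient remains in the study.

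**Time over which the conflict can arise**

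In the main study the product is used in Months 1 to 3, and then "During the following 3 months (Months 4 through 6), use of Abilify MyCite will be prohibited". An optional period of up to 6 months may follow Day 180. In the exploratory study each sequence has four months of use, for example "Sequence 1: Only in Months 1, 2, 5, and 10".

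- Main study to Day 180: 90/180 = 50%.
- Main study with the whole optional period used: (90 + 180)/360 = 270/360 = 75%.
- Exploratory study, either sequence: 4/12 = 33%.

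These are ceilings, because Section 3.5.1.5 lets the product be stopped as clinically appropriate. Off product, 3.6.3 alone governs and the patient is withdrawn.

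**Size of the effect on the primary proportion**

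Inputs from Protocol 7.1 and SAP 4.2: 447 MyCite completers, and planned proportions of 29.04% (MyCite) and 36.30% (control). The planned difference is 36.30 - 29.04 = 7.26 points. Expected MyCite events are 447 × 0.2904 = 129.8.

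If *k* patients are kept rather than lost, and *h* of them are hospitalized, the MyCite proportion becomes (129.8 + *h*)/(447 + *k*). The documents give no pregnancy rate, so the values of *k* are assumptions.

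| *k* | *h* | Proportion | Shift (points) |
|---|---|---|---|
| 1 | 1 | 130.8/448 = 29.20% | +0.16 |
| 1 | 0 | 129.8/448 = 28.98% | -0.06 |
| 5 | 5 | 134.8/452 = 29.82% | +0.78 |
| 5 | 0 | 129.8/452 = 28.72% | -0.32 |

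Even the extreme case, five patients all hospitalized, is about a tenth of the planned difference (0.78/7.26 = 0.11).

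**The case against.** The strongest reply concerns study participation. Section 4.5 never says that a patient who continues the product stays in the study. The product is commercially available, so a physician could withdraw the patient under 3.6.3 and go on prescribing it. The exception clause, which allows departures from study discontinuation only in life-threatening conditions, suggests that withdrawal was meant as the default. This reading is possible and narrows the conflict with 3.6.3. It leaves the conflict with 4.1.4 untouched, and it does not explain why 4.5 ties withdrawal to the physician's stopping the product. If withdrawal was meant as the default, 4.5 is unclear within itself as well.

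A second reply is that safeguards exist. Confirmed pregnancy is immediately reportable (4.1.4, 4.3), pregnancies are followed to term, and infants are followed for at least 6 months (4.5). Section 3.7 describes deviations narrowly and provides for a joint decision by physician and sponsor after a significant one. These provisions do limit the harm. But 3.7 still counts departures from Good Clinical Practice as deviations, and its joint decision settles a case after the event without giving sites one rule beforehand.

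A third reply is that the numerical effect is slight and rests on assumed counts. That is correct. SAP 5.0 records that the trial stopped after two subjects with no efficacy assessment, so the primary result was not affected in practice. The case for correction rests on the contradictory safety instruction.

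Finally, the choice of rule is open to argument, since 4.5 ties continuation to treatment guidelines. That bears on which way to harmonize the sections, and they need harmonizing either way.

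**Conclusion.** The concern holds. On a pregnancy confirmed on product, Section 4.5 contradicts 4.1.4 on treatment. It also departs from 3.6.3 on study participation, both by making withdrawal conditional and by adding an exception that 3.6.3 lacks. The visible text sets no order of precedence. The conclusion rests on current, unredacted protocol wording and on no outside source.

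This is a contradiction in a safety instruction that should be corrected, with limited reach. It applies only during product use, existing reporting and follow-up reduce the harm, and its effect on the primary proportion would be small under the assumed one to five patients. Early termination made the practical effect minimal but does not make the text consistent.

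**What to change.** Replace the continuation sentence in Section 4.5, and the conditional sentence after it, with a single rule consistent with 4.1.4 and 3.6.3. For example:

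> *Once pregnancy is confirmed, Abilify MyCite must be stopped safely (by tapering, or by a move to other suitable treatment, as the patient's safety requires). The patient is withdrawn from the study under Section 3.6.3, and the pregnancy is followed to term.*

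State the life-threatening-condition exception once, in 4.5. Say whether it covers the product, study participation or both, and cross-reference it from 3.6.3 and 4.1.4. This direction follows two of the three sections and the pregnancy exclusion in 3.3.5, and oral aripiprazole or other care remains available to the patient. If the sponsor's safety function prefers physician discretion, amend 4.1.4 and 3.6.3 to match 4.5 instead.

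The cost is one replaced passage and two cross-references in a protocol amendment, with no added visits, procedures or patients. The consent text is not among the documents supplied, so whether it also needs a change is not judged here.
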